## 8.2 Main Endpoints

### 8.2.1 Primary Endpoints

- *P. falciparum* functional activity as measured by DSF (Arms 3c/3d)

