## 17.2 Main Study

### 17.2.1 Primary Objective

To assess vaccine activity of Pfs230D1M-EPA/AS01 against *P. falciparum* transmission by direct skin feeding assay (DSF) (Arms 1a/1b and 3c/3d only)

A Poisson type model with compound level clustering with offset for the number of DSF tests that were performed will be used. The primary analysis of activity measured by DSF will be the Poisson GEE, which will be performed on the data once with Pm/Po midguts, and once without. The proportion of subjects infecting at least 1 mosquito in at least 1 DSF over the primary analysis period following dose 3 will be compared by use of a GEE model for binary response with compound level clustering.

Each of the above analyses will be performed on the subsample of subjects that had a concurrent positive BS (any parasite sexual and/or asexual) or rapid test positive with their DSF results.

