### 17.2.2 Secondary Objectives

To assess vaccine efficacy of Pfs230D1M-EPA/AS01 against *P. falciparum* infection measured by BS (All Arms except Arms 3e/3f)

The vaccine efficacy will be assessed by comparing the rates of positive BS in children 5-18 years of age receiving Pfs230D1M-EPA/AS01 vs those receiving the comparator vaccines. An additional measure of vaccine protection will be assessed in the participants 1-4 years of age in Arms 4a/4b by comparing the rates of positive BS in the compounds receiving Pfs230D1M-EPA/AS01 vs those receiving the comparator vaccines.

To assess safety and reactogenicity of administration of Pfs230D1M-EPA/AS01 (All Arms)

- The frequency of systemic and local AEs will be summarized.
- A line listing of each clinical and laboratory AE classified as local, solicited, or other will be displayed in tables stratified by vaccine allocation.
- AEs will be summarized by severity and relationship to vaccine.
- The proportion of subjects with at least 1 AE will be compared by study group, and tests will be performed to assess whether these groups differ with respect to these proportions. To evaluate the difference in AEs between the initial vaccination and the subsequent vaccinations, a WSRT will be performed, where the response for each subject is the difference between the numbers of AEs in the 7 days following each vaccination. To compare number and severity of AEs between control and vaccine arms, the Wilcoxon-Mann-Whitney test (WMW, also known as Wilcoxon rank sum test and Mann-Whitney U test) as well as linear regression may be used.
- SAEs occurring within the study period will be listed by relationship to vaccine.

ELISA and SMFA assays will be conducted on a subset of samples deemed to be of scientific interest by DSF or BS assays due to the intensive laboratory analysis required to generate the data. Analysis of these data will take into account the compound randomization.

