### 17.3.2.3 Analysis

The primary DSF analysis will use a GEE model with compound level clustering and the number of positive DSFs as outcome will be used for analysis with an offset for the number DSF tests. The primary parasitemia analysis will be analogous. The primary analysis population will follow the intention-to-treat principle. Additional analyses will explore the effects of different covariates such as time since start of the rainy season, SMC treatment, compound-level vaccine coverage, or proximity to a control compound on vaccine efficacy.

The primary safety and immunogenicity analyses will compare the rates of AEs or levels of antibody/activity between vaccinated and control individuals using standard statistical methods that respect compound-based randomization, as appropriate.

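### The primary skin-feed analysis is run with and without P. malariae/P. ovale midguts, and the plan does not say which result decides

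*Combined protocol and SAP*

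**What the plan says.** Section 17.2.1 sets the main-study primary objective as vaccine activity against P. falciparum transmission by DSF. Section 8.2.1 gives the matching endpoint as P. falciparum "functional activity as measured by DSF (Arms 3c/3d").

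On the analysis, 17.2.1 designates as primary "the Poisson GEE, which will be performed on the data once with Pm/Po midguts, and once without". It adds that the proportion of children with at least one infecting feed "will be compared by use of a GEE model for binary response with compound level clustering". It closes with: "Each of the above analyses will be performed on the subsample of subjects that had a concurrent positive BS", where the smear may show any parasite stage and a positive rapid test also qualifies.

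Section 17.3.2.3 restates the primary DSF analysis as a GEE on the number of positive feeds, with an offset for feeds performed, and adds: "The primary analysis population will follow the intention-to-treat principle". It does not mention species. Section 12.6.5.2 scores a mosquito as positive on one or more oocysts, whatever the species. Section 3.3.3 reports that oocyst speciation of the 70 positive Year 1 feeds was still pending and that the study remained blinded.

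**The concern.** A primary analysis should yield one result that decides the claim. Here the word primary covers two. If they disagree, the plan gives no way to say whether vaccine activity was shown. The general scoring rule in 12.6.5.2 pulls towards counting every oocyst, while the objective and endpoint pull towards P. falciparum only.

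The two runs also estimate different things. The antigen is a P. falciparum protein (section 1.1). A feed that is positive only through Pm/Po is not P. falciparum transmission, and counting it adds events on which no effect is expected. The question is a practical one: section 1.2.2 describes household clusters of non-falciparum infection in Mali.

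A related labelling gap follows in the same section. All the analyses are repeated in children with a concurrent positive smear or rapid test, and nothing says what those results are for. Positivity is observed after randomisation. The trial's own hypothesis is that vaccinating a compound reduces infection among its members (sections 1.2.2 and 17.2.2), so test-positive children in the two arms may not be comparable.

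**Working it through.** **Which choices are fixed.** Model: fixed (Poisson GEE, 17.2.1, restated in 17.3.2.3). Population: fixed (intention-to-treat, 17.3.2.3). Species rule: not fixed anywhere. That leaves two candidate primary results.

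**The plan's own figures.** Table 17 needs 64 DSF-positive children for 0.8 power at vaccine activity (VA) 0.5. The Schoenfeld formula, two-sided 0.05 and 1:1, gives 4(1.960 + 0.842)² / [ln(1 − 0.5)]² = 65.3, so 66. At VA 0.6 it gives 38 against 40 in the table, and at VA 0.4 it gives 121 against 115. The table comes from simulation, so these differences are not treated as errors. The alpha and type I error printed beside the table are garbled; 0.05 two-sided is assumed here, as in 17.3.2.2.

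**Assumptions for the size.** Let s be the share of comparator-arm positives that are Pm/Po only. The documents give no value, so s = 0.05 to 0.20 is assumed, with no vaccine effect on Pm/Po and a true VA of 0.50 on P. falciparum.

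**Dilution in the with-Pm/Po run.** Set comparator positives to 1. Vaccine-arm positives are then (1 − s)(1 − VA) + s = 1 − VA(1 − s), so apparent VA = VA(1 − s).
- s = 0.05: 0.50 × 0.95 = 0.475.
- s = 0.20: 0.50 × 0.80 = 0.40.

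**Events needed**, relative to the P. falciparum-only run: [ln(1 − VA) / ln(1 − VA(1 − s))]².
- s = 0.05: (0.693 / 0.644)² = 1.16.
- s = 0.20: (0.693 / 0.511)² = 1.84.

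**Events gained.** Counting Pm/Po also adds positives. Total over both arms is 2 − VA(1 − s), against (1 − s)(2 − VA) for P. falciparum alone.
- s = 0.05: 1.525 / 1.425 = 1.07.
- s = 0.20: 1.60 / 1.20 = 1.33.

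**Net cost in children.** 1.157 / 1.070 = 1.08, and 1.841 / 1.333 = 1.38. This applies only if the with-Pm/Po run alone decides.

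**Type I error if either run may be claimed.** The runs share most of their events, so the correlation of the two test statistics is roughly √(1 − s): 0.975 at s = 0.05 and 0.894 at s = 0.20. The bivariate normal probability that at least one exceeds 1.96 in absolute value is 0.060 and 0.071. The figure for two independent tests, 1 − 0.95² = 0.0975, does not apply.

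A null simulation of a compound-clustered Poisson model with robust variance agrees. It used 384 children, 100 compounds, 8 feeds, intra-subject correlation 0.14, 12% seasonal positivity and 3,000 runs. It gave 0.066, 0.064 and 0.079 for shares of 5, 10 and 20%; single-run rates at these shares were 0.052 to 0.063.

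**The case against.** The best reply is that the objective and endpoint already name P. falciparum, so the run without Pm/Po is the natural primary. The other run would then be there because 12.6.5.2 scores any oocyst. Both runs are prespecified and the data are blinded, so what is missing is a label. Most of this stands. It points to the right answer, but the plan does not state it, and 17.2.1 gives both runs the same status.

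Four stronger readings are tempting, and the documents do not support them.
- A reader might infer that all the listed analyses compete as primary: two Poisson runs and one binary model, each in two populations. They do not. The Poisson GEE is named over the binary model, and intention-to-treat excludes the test-positive subset from the primary population.
- A reader might infer that the subset is defined by the trial's secondary endpoint, since 17.2.2 sets out "To assess vaccine efficacy of Pfs230D1M-EPA/AS01 against *P. falciparum* infection measured by BS". The two overlap but differ. The endpoint in 8.2.2 is asexual P. falciparum parasitemia by smear; the subset accepts any parasite stage or a rapid test, and 12.5.2 bars rapid tests from replacing microscopy for parasitemia status.
- Table 17 invites the statement that dilution from VA 0.50 to 0.40 raises the requirement from 64 to 115 positive children. That ignores the extra positives the with-Pm/Po run collects; the net factor is at most about 1.38 here.
- The two costs should not be added. Dilution matters only if the with-Pm/Po run alone decides. Type I inflation arises only if either run may be claimed, and then the undiluted run is available.

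On the subset, the vaccine acts in the mosquito (section 1.1), so any effect on a vaccinee's own smear is indirect, through less transmission in the compound. The possible selection is real in principle, but its size cannot be derived from the documents.

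**Conclusion.** The point holds in this form: one element of the primary analysis, the species rule, is left open between two results, and one of the two does not estimate the stated endpoint. The error-rate consequence is modest, about 1 to 2 percentage points above 5%. The power consequence is at most moderate, a factor of 1.08-1.38 in children. Both sizes rest on the assumed 5-20% share and on no vaccine effect on Pm/Po. The finding that no rule decides rests on the text alone and needs neither assumption.

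The main harm is that the result on the only main-study primary endpoint is undefined if the runs disagree. With 45 DSF-positive children in Year 1 (17.3.2.1) against 64 needed at VA 0.5, a borderline result is plausible. Choosing the rule after unblinding would not be credible.

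**What to change.** In 17.2.1, before unblinding, state that the sole primary analysis is the intention-to-treat Poisson GEE counting only P. falciparum-positive midguts. Midguts with Pm/Po only count as negative, so their feeds stay in the offset. Describe the with-Pm/Po run as a sensitivity analysis. Repeat the species rule in 17.3.2.3 so that the two sections agree.

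Label the analyses in children with a concurrent positive smear or rapid test as supportive only. Note there that they condition on a post-randomisation variable which the vaccine may affect indirectly through reduced compound-level transmission.

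The cost is a few sentences. No extra laboratory work follows, because the run without Pm/Po already needs speciation. The event count should then be tracked on P. falciparum positives: if 5-20% of the 45 Year 1 children were Pm/Po only, 45 × 0.95 to 45 × 0.80, or about 43 to 36, would remain.

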### 17.2.2 Secondary Objectives

To assess vaccine efficacy of Pfs230D1M-EPA/AS01 against *P. falciparum* infection measured by BS (All Arms except Arms 3e/3f)

The vaccine efficacy will be assessed by comparing the rates of positive BS in children 5-18 years of age receiving Pfs230D1M-EPA/AS01 vs those receiving the comparator vaccines. An additional measure of vaccine protection will be assessed in the participants 1-4 years of age in Arms 4a/4b by comparing the rates of positive BS in the compounds receiving Pfs230D1M-EPA/AS01 vs those receiving the comparator vaccines.

To assess safety and reactogenicity of administration of Pfs230D1M-EPA/AS01 (All Arms)

- The frequency of systemic and local AEs will be summarized.
- A line listing of each clinical and laboratory AE classified as local, solicited, or other will be displayed in tables stratified by vaccine allocation.
- AEs will be summarized by severity and relationship to vaccine.
- The proportion of subjects with at least 1 AE will be compared by study group, and tests will be performed to assess whether these groups differ with respect to these proportions. To evaluate the difference in AEs between the initial vaccination and the subsequent vaccinations, a WSRT will be performed, where the response for each subject is the difference between the numbers of AEs in the 7 days following each vaccination. To compare number and severity of AEs between control and vaccine arms, the Wilcoxon-Mann-Whitney test (WMW, also known as Wilcoxon rank sum test and Mann-Whitney U test) as well as linear regression may be used.
- SAEs occurring within the study period will be listed by relationship to vaccine.

ELISA and SMFA assays will be conducted on a subset of samples deemed to be of scientific interest by DSF or BS assays due to the intensive laboratory analysis required to generate the data. Analysis of these data will take into account the compound randomization.

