If there are no safety concerns, in a staggered manner, the main phase will begin enrollment of approximately 137 compounds/vaccine units (~1500 vaccinees + ~400 under 5 years of age for parasite surveillance). Children enrolled during the pilot safety phase will join their main phase compounds/family for vaccination #3. Prior to receipt of first vaccination, all subjects will receive a full treatment course of AL. All vaccinated subjects will be monitored for safety and tolerability. Immunogenicity outcomes will be antibody responses as measured by enzyme-linked immunosorbent assay (ELISA) against recombinant Pfs230D1M. Functional activity of the induced antibodies will be assessed by standard membrane feeding assays in select samples. Vaccine activity will be measured in children 9-18 years of age who will undergo direct skin feeds (DSF) starting 2 weeks post vaccination #3 for a total of 8 DSFs.

Prior to scheduled last vaccination in members of the compound/family, children 1-4 years of age and vaccinated children 5-8 years of age will receive a full treatment course of AL prior to the expected start of the transmission season and will then be followed every 2 weeks by blood smear (BS) along with all vaccinated children. Children 9-18 years of age will also be assessed for vaccine efficacy, but as a separate analysis from those 1-8 years of age.

In Year 2, those who received vaccination during Year 1 (5 years of age and older at enrollment), if eligible and still on study, will receive a single fourth vaccination per their vaccine unit (VU) blinded arm assignment. No new individuals will be enrolled. Again, children 1-4 years of age and vaccinated children 5-8 years of age will receive a full treatment course of AL prior to the expected start of the transmission season and will then be followed every 2 weeks by BS along with all vaccinated children. Children 9-18 years of age will also be assessed for vaccine efficacy against parasitemia, but as a separate analysis from those 1-8 years of age. Immunogenicity outcomes will be antibody responses as measured by ELISA against recombinant Pfs230D1M. Functional activity of the induced antibodies will be assessed by standard membrane feeding assays in select samples. Vaccine activity will be measured in children 9-18 years of age who will undergo DSF starting 2 weeks post vaccination #4 for a total of 10 DSFs.

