administered prior, subject to clinician's discretion. Children 1-4 years of age will be enrolled just before the malaria transmission season and will receive AL concomitantly with children 5-8 years of age who will be treated ~14 days before the 3rd vaccine dose and ~7 days prior to vaccination #4. All enrolled subjects (except adults,  $\geq 19$  years old) will be monitored for patent parasitemia every 2 weeks, and all enrolled subjects during unscheduled visits if clinically indicated, for at least 6 months up to 12 months post vaccination, with time to patent parasitemia being evaluated as a vaccine efficacy timepoint in children 1-8 years of age as well as 9-18 years of age within the compounds (separate secondary evaluation given expected nighttime mobility and no pre-transmission season AL treatment). Preteen and adolescent subjects will also be assessed by DSF for vaccine activity starting 2 weeks post receipt of vaccination #3 and post receipt of vaccination #4; DSFs will be completed every 2 weeks for a total of 8 DSF (post vaccination #3) and for a total of 10 DSF (post vaccination #4).

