## 12.5 Malaria Diagnostics

### 12.5.1 Blood Smears (BS)

The gold standard for malaria diagnosis is the detection of malaria parasites on Giemsa-stained thick blood films. Giemsa stained thick and thin films will be examined for asexual and sexual parasites in the MRTC clinical laboratory, as outlined in [Appendix A](#). BS are prepared in duplicate according to standard procedures and evaluated by trained study microscopists.

For detection of gametocytemia, counts are reported per 1,000 WBCs. A positive gametocyte read is defined as a single, confirmed gametocyte seen by one reader and confirmed by the other microscopist per 1,000 WBCs.

Thick BS may be prepared from the blood remaining in the venous cannula, or (at time points when no venous blood collection is planned) from a finger prick or venous blood sample at the subject's request.

Thin/thick BS will be used for detection of *P. falciparum* parasitemia as a primary efficacy endpoint for the main phase of the trial, and for malaria diagnosis throughout the study.

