### 17.3.2.2 Vaccine Efficacy

Vaccine efficacy will be measured by blood smear (BS) and detection of asexual Pf parasitemia. The background infection rate in the population is measured as the proportion of individuals from a recent PfSPZ trial (NIAID Protocol #16-I-N004) with any BS+ during follow up. Using this as the rate of background infection we can calculate power under various scenarios using as endpoint parasitemia positivity over the season. We use simple binomial tests with  $\alpha = .05$  two-sided and ignore the anticipated negligible effects of compound level clustering. Sample sizes are multiplied by an inflation factor of two to adjust for potential compound level contamination of the vaccine effects due to mixing of mosquitoes or movement of vaccinees. We see that with a minimum of 350 total subjects 1-8 years of age that are randomized and do not drop out, we have power to detect VEs of 30% or greater within this age group alone based on the risk of first infection. We will analyze subjects 9-18 years of age based on the proportion of positive blood smears.

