**Table 18. Vaccine Efficacy Sample Size Power Calculations Based on Predicted Vaccine Efficacy**

Background Infection Rate	VE	Power	Total Sample Size	Total Sample Size per Arm After Adjustment for mosquito-human contamination
70%	20%	80%	375	750
70%	25%	80%	242	484
70%	30%	80%	172	343
70%	35%	80%	128	256
70%	40%	80%	98	196

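### The smear-efficacy comparison in Section 17.2.2 (ages 5-18, with 1-4 as an extra) is not the drug-cleared 1-8 first-infection analysis that the design sets up and powers

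*Combined protocol and SAP*

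**What the plan says.** Section 17.2.2 sets the main-study efficacy comparison as "comparing the rates of positive BS in children 5-18 years of age receiving Pfs230D1M-EPA/AS01 vs those receiving the comparator vaccines". It then treats the 1-4 year-olds of Arms 4a/4b as a further measure. It names no 1-8 analysis and no 9-18 analysis.

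Elsewhere the age boundary lies between 8 and 9:

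- **Précis**, for both years: "Children 9-18 years of age will also be assessed for vaccine efficacy, but as a separate analysis from those 1-8 years of age".
- **Section 7.1**, repeated in 7.2.2: "with time to patent parasitemia being evaluated as a vaccine efficacy timepoint in children 1-8 years of age". Ages 9-18 are a separate secondary evaluation because of night-time mobility and the absence of AL before the season.
- **Sections 7.1 and 7.2.2** give AL to ages 1-8 about 14 days before dose 3; Section 7.1 adds a course about 7 days before dose 4. **Section 1.2.3** says ages 9-18 get none before either dose, because AL suppresses positive skin feeds.
- **Section 17.3.2.2** bases power on at least 350 children aged 1-8 and the risk of first infection, then adds: "We will analyze subjects 9-18 years of age based on the proportion of positive blood smears".

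Section 17.3.2.3 says only that the parasitemia analysis will mirror the skin-feed model, which takes a count of positives with an offset. It gives no age grouping. Section 12.5.1 describes blood smear "as a primary efficacy endpoint for the main phase of the trial", whereas Sections 6.2.2 and 8.2.2 list it as secondary.

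**The concern.** The extra AL courses in ages 1-8 serve to make a later positive smear a new infection. A transmission-blocking vaccine cannot remove an infection that the child already carries. Grouping ages 5-8 with ages 9-18 therefore combines children re-treated just before the key doses with a larger group who were not, and efficacy is pulled toward zero.

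The analysis that the sample size was built for also has no place in the analysis section. The endpoint takes several forms: a rate of positive smears (17.2.2), a count with offset (17.3.2.3), time to patent parasitemia (7.1, 7.2.2), risk of first infection (17.3.2.2) and prevalence (1.2.3.1.1.1). With grouping and form both open, the choice could be made after unblinding.

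**Working it through.** **1. Reproduce the plan's figure.** Section 17.3.2.2 uses simple binomial tests at 0.05, "two-sided and ignore the anticipated negligible effects of compound level clustering". The design row of Table 18 reads "70% 30% 80% 172 343": background 70%, efficacy 30%, power 80%, total 172, and 343 after adjustment. The adjustment is stated: "Sample sizes are multiplied by an inflation factor of two to adjust for potential compound level contamination of the vaccine effects".

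With p1 = 0.70, p2 = 0.70 × 0.70 = 0.49 and mean 0.595, the pooled-variance formula gives, per arm:

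n = [1.96 × √(2 × 0.595 × 0.405) + 0.842 × √(0.70 × 0.30 + 0.49 × 0.51)]² / 0.21² ≈ 84.6

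The total is about 169 (170 after rounding up per arm), doubling to about 338, against the stated 172 and 343. The other rows agree within 3% or 2 subjects. The last column is headed as per arm, but its values reproduce only as totals.

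**2. Power by age group.** Same test, efficacy 30%, total N halved for contamination and split between two arms (N/4 per arm):

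| Group | N | Power |
|---|---|---|
| 1-8, planned | 350 | 81.3% |
| 1-8, enrolled (192 + 215, Table 12) | 407 | 86.8% |
| 5-18, enrolled (215 + 399) | 614 | 96.6% |

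The last row holds only if the 70% rate of new infection also applies to ages 9-18, which the documents do not state.

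**3. Share not re-treated.** 399 / 614 = 65%. These children do receive AL at day -7. Dose 3 is at day 56 (main) or day 126 (pilot), so the gap is 63 days (9 weeks) or 133 days (19 weeks). No AL is scheduled for them in Year 2.

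**4. Carry-over visible in Table 8 (Section 3.3.1.5), ages 9-18.** Smear-positive after dose 1: 28. After dose 2: 83 of 391. After dose 3: 275 of 386.

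- If all 83 persisted: 83 / 275 = 30% of post-dose-3 positives.
- If the 28 are added with no overlap: 111 / 275 = 40%.

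Both figures ignore treatment, so they are the most these smears suggest.

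**5. Effect on a true efficacy of 30%.** Let f be the share of 9-18 control-arm positives that are carry-over, equally frequent in both arms. Apparent efficacy in ages 9-18 is then 0.30 × (1 − f). With headcount weights of 0.35 and 0.65:

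- f = 0.30: 0.35 × 0.30 + 0.65 × 0.30 × 0.70 = 0.242
- f = 0.40: 0.35 × 0.30 + 0.65 × 0.30 × 0.60 = 0.222

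Headcount weights assume equal control-arm positivity in the two age groups. Weighting instead by Table 8 post-dose-3 positives, with both arms blinded together (109 in ages 5-8, 275 in ages 9-18; weights 0.284 and 0.716), gives 0.236 and 0.214. The conclusion does not change.

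**The case against.** **Section 17.2.2 can be read as separating vaccinated from unvaccinated children.** Ages 1-4 are unvaccinated and receive monthly seasonal chemoprevention, so looking at them apart is reasonable. The section does not prescribe a single unstratified model, and the separate-analysis statements elsewhere remain in force. This supports stratifying by 1-4 versus 5-8. It does not supply the missing 1-8 analysis, and the stated 5-18 comparison crosses a boundary drawn in four other places.

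**A reader might infer that the 9-18s were never cleared.** The documents say otherwise: every vaccinee aged 5 or over gets AL at day -7. What ages 9-18 lack is the second course and any course in Year 2.

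**A reader might infer a much larger bias.** In the formula above, an apparent efficacy of about 15% would need 75% of 9-18 positives to be carry-over. Table 8 does not support that for Year 1. Because symptomatic malaria is treated (Section 12.5.1.1), the true share may be below 30%.

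**A reader might infer lost power.** Pooling raises N, so nominal power is not reduced. Ages 1-4 alone (192 enrolled) would have about 56% power on Table 18's assumptions, but the plan claims no power for that comparison. Section 1.2.4 also reports 58% patent parasitemia in children on chemoprevention, so the 70% rate may not apply.

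**Counting repeat positives is not wrong in itself.** Section 1.2.3.1.1.1 describes the smear endpoint as a prevalence, which a count with offset can represent. The fault is that no form is assigned to each age group.

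**The endpoint is secondary.** The primary skin-feed analysis is unaffected. The label in Section 12.5.1 may only mean the main efficacy measure as opposed to vaccine activity, so it needs a wording correction and no more.

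**Conclusion.** The contradiction stands on the text alone. Section 17.2.2 as written omits the powered 1-8 first-infection analysis and replaces it with a 5-18 comparison in which 65% of children have no AL before dose 3 or 4. Section 17.3.2.3 does not repair this.

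The consequence is a diluted estimand: a true efficacy of 30% reads as roughly 24-22%. That range assumes that 30-40% of 9-18 positives are carry-over, equally frequent in both arms, and that the 1-8s are fully cleared. Sub-patent and Year 2 carry-over could be larger, but the documents give no figure.

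**What to change.** Before unblinding, revise the following:

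- **Section 17.2.2:** make the main efficacy analysis first positive smear in all 1-8 year-olds (Arms 2a/2b, 3a/3b, 4a/4b), by a method that accounts for vaccine-unit clustering, stratified 1-4 versus 5-8. A Cox model with robust variance is one option.
- **Start of follow-up:** state one date, at or after dose 3 (dose 4 in Year 2). Starting at the preceding AL course would count infections from about two weeks before dose 3, whereas Section 1.2.3 says blocking activity exceeds controls only after that dose.
- **Two years:** give one rule for combining Year 1 and Year 2 first infections in the same child.
- **Ages 9-18:** report separately as the proportion of positive smears, and limit the analogy in Section 17.3.2.3 to that analysis.
- **Supportive analyses:** keep any 5-18 or 1-4-only comparison, labelled as supportive.
- **Section 12.5.1:** align the label with the secondary status in Sections 6.2.2 and 8.2.2.

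The cost is wording only, since the smears are already in the visit schedule.
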